
Participant Compensation:

Once participants are deemed eligible to be enrolled in the study (following baseline assessments) the total monetary compensation provided to participants in this study will be \$700. They will be provided

\$200 upon completion of the first 4 weeks of the trial, \$200 after completion of the 12 week medication phase and \$300 after completion of the follow-up period.

Due to the frequent visits required to CAMH, participants will also be provided with TTC tickets (or its cash value if preferred by participants) during treatment and follow-up visits as required.

Contingency Management

Participants will be provided with a \$5 voucher for each visit where a sample of urine or blood is collected, however for each missed appointment, a \$5 value will be subtracted from the total amount. These vouchers will be provided at two separate times, after completion of the treatment phase of the study, and after completion of the follow-up period.

In order to engage participants and to maximize returns to CAMH for weekly visits, a "fish-bowl prize" system will be instituted where during each visit participants will have a chance to reach within a large bowl/drum and select a ticket which provides a chance to win a prize. These prizes will range from tickets containing motivational messages, a small prize such as a pen or notepad, a \$5 gift card to Tim Hortons up to a to a maximum prize of \$50 in the form of a gift card to a number of establishments including restaurants, grocery stores, or retail merchants.

Data analysis: All analyses will be implemented in SPSS v24.0. Associations with p-values of less than 0.05 will be considered statistically significant, and all tests will be 2-sided. The data will be screened prior to analysis to ensure that the underlying assumptions for all subsequent statistical procedures are met. Preliminary analyses will include chi-square tests, t-tests, and Mann-Whitney U tests.

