Our Primary outcome measures will be: 1) tolerability which will be assessed by determining the number of participants who withdraw from the study because of SAEs and 2) pilot efficacy of this intervention will be assessed by assessing seven-day point prevalence cannabis abstinence one week after the end of medication phase; and at 3 month follow up. Secondary outcome measures will be: 1) percentage of days of cannabis use over the study duration until the 3 month follow up; 2) amount of cannabis use over the study duration until the 3 month follow up; 3) effects on withdrawal symptoms scores, craving scores and number of urine samples screen as positive and 4) DSM5 criteria for CUD at the end of treatment and follow-up as compared with baseline. Efficacy analyses of count variables (e.g. number of joints per week) will be performed using generalized estimating equations (GEEs), specifying a negative-binomial distribution for the counts. Linear mixed models will be used to analyze continuous, secondary outcome measures (e.g. mood and anxiety ratings, physiological measures). All efficacy analyses will be by intention-to-treat. Treatment week will measure changes within-subjects. Subjects will be use as a measure of abstinence in this study. Urine samples will be collected and analyzed for THC metabolites.

Procedure for accounting for missing, unused, and spurious data: In the final report the procedures used to deal with missing, unused or spurious data in statistical analyses will be described.

Procedures for reporting deviations from the original statistical plan: Any deviation from the planned statistical analyses will be described in the final report.

Power calculation: The goal is to collect pilot data to demonstrate tolerability and trend for efficacy of Vivitrol® for treatment of cannabis dependence. We are hypothesizing that the use of cannabis will decrease by at least 50% after treatment with Vivitrol®. Assuming Cannabis use of around 9.5 g (SD = 5) at baseline [as per paper], a sample of 10 subjects will give us 80% power to detect a decrease in cannabis use of 50% from baseline to the last time point. The power calculation was conducted through Monte Carlo simulation, where 5000 replications were conducted. It was also assumed that the

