correlation between baseline and the last time point was 0.6. A Mixed Effect Model was adjusted for each replication, where Time was the only Fixed Effect and Subjects entered the model as Random Effects. The power in such simulation is defined as the proportion of the replications where the Time effect is significant at confidence level 0.05 and two tailed test. No dropout was assumed.

Termination of the Study

Reasons for withdrawing individual subjects from the study may include one or more of the following:

- 1) Severe side effects;
- 2) Major protocol deviation;
- 3) Subject lost to follow-up;
- 4) Withdrawal of consent;
- 5) Pregnancy

Any subject may be discontinued from the study at the discretion of the investigators if it is deemed to be in the best interest of the subject.

Study Documentation

Investigators will retain a subject identification code list if they need to contact subjects after the study. This list will contain the complete name, identification number, address and phone number of all subjects and will be held confidentially at the investigators site after completion of the study.

A CRF will be completed for each subject enrolled in the study. A subject screening log, noting reasons for screen failure, where applicable, will be maintained for all subjects. All information recorded on the CRFs for this study will be consistent with the subject's source documentation (e.g. medical records). The investigator will document the obtained informed consent and record all medication administration, medical history, results of laboratory tests and adverse events in the CRF. Laboratory printouts and psychometric assessments will be considered source documents and will be incorporated into the CRF without transcription in a confidential manner.

The data collected during the study will be typed or written onto the CRF and other study documents using a ballpoint pen. If an error is made, it will be crossed out with a single horizontal line, and the new information clearly recorded next to the error, initialed and dated. Correction fluid is not allowed at any time.

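### Secondary count outcomes are to be tested by negative-binomial GEE in 10 subjects with no small-sample method named; the usual uncorrected robust Wald test would have about 10% type I error, not 5%

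*Combined protocol and SAP*

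**What the plan says.** The combined protocol and SAP describes an open-label study with one treated group of 10 and no control (Overview). Under Data analysis, efficacy outcomes that are counts, with weekly joints as the example, go to "generalized estimating equations (GEEs), specifying a negative-binomial distribution for the counts". Continuous secondary outcomes go to linear mixed models, which are not in question here. The effect of interest is described only as "Treatment week will measure changes within-subjects". The decision rule is "Associations with p-values of less than 0.05 will be considered statistically significant, and all tests will be 2-sided", and on software the section says "All analyses will be implemented in SPSS v24.0".

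The section does not state the GEE covariance estimator, the working correlation, the reference distribution, the coding of week, or any adjustment for the small number of subjects. It does say that data will be screened for the assumptions of each procedure and that deviations from the plan will be reported.

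The Power calculation is a separate matter. It uses a mixed model on grams of cannabis and claims "80% power to detect a decrease in cannabis use of 50% from baseline to the last time point" with 10 subjects.

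**The concern.** GEE inference rests on the number of independent subjects, not the number of visits. The robust variance is built from subject-level residuals, and with few subjects it is too small on average. Referring the result to a normal or chi-square distribution also ignores the uncertainty in that variance. Both errors make the test too liberal, and 10 subjects is well inside the range where this matters.

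For any outcome analysed this way, a change in use could be declared about twice as often as the stated 5% when there is none. The coding of week matters too: left open, it permits anything from one trend to a joint test with more contrasts than the data can support.

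**Working it through.** **Inputs from the documents.** n = 10, one arm (Overview); two-sided 0.05 (Data analysis); "Assuming Cannabis use of around 9.5 g (SD = 5) at baseline" and "correlation between baseline and the last time point was 0.6" (Power calculation); weekly cannabis assessments (Summary of Study Assessments).

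**Assumptions.** The documents give no mean or SD for joint counts. The simulations use weekly means of 5 to 60 and several dispersions. The two-visit runs carry over the coefficient of variation (CV) in grams, 5/9.5 = 0.53, and the 0.6 correlation, with CVs of 0.75 and 1.0 as heavier cases.

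**1. The plan's own figure.** SD of change = 5 × √(2 × (1 − 0.6)) = 4.47 g. A 50% fall is 4.75 g, so d = 4.75/4.47 = 1.062. A two-sided paired t-test with n = 10 (equivalent to the described mixed model with two complete time points) has 84.7% power, and n = 9 gives 79.6%. Ten subjects therefore do reach 80%. This calculation does not involve the GEE.

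**2. One contrast, uncorrected robust Wald, closed form.** With complete pairs the robust variance divides the sum of squared subject-level deviations by n², where the t-test divides by n(n − 1). Hence z ≈ t × √(n/(n − 1)), and

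error = P(|t(n−1)| > 1.96 × √((n − 1)/n)).

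| Subjects | Threshold on t | Type I error |
|---|---|---|
| 10 | 1.96 × √(9/10) = 1.859 | 9.6% |
| 8 | 1.96 × √(7/8) = 1.833 | 10.9% |
| 7 | 1.96 × √(6/7) = 1.815 | 12.0% |
| 50 | 1.96 × √(49/50) = 1.940 | 5.8% |

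The last row shows that the excess comes from having few subjects.

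**3. One contrast, simulated counts, n = 10.** Two visits, correlation 0.6, 40,000 replicates per scenario:

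- CV 0.53: 9.9-11.1%.
- CV 0.75 to 1.0: 10.4-14.6%.

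A separate set of simulations, covering baseline versus last visit and a linear week effect, gave 9.6-15%. A cross-check with strongly autocorrelated weekly data gave 15.1% (exchangeable working correlation) and 16.7% (independence). With a linear week effect, 50 subjects gave 5.9% and 100 gave 5.7%.

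**4. Week as a factor.** Weeks 1-12 alone give 12 − 1 = 11 contrasts; baseline plus weeks 1-12 give 12. The robust covariance of those contrasts is a sum over 10 subjects whose contributions add to zero, so its rank is at most 10 − 1 = 9. A 12 × 12 matrix computed from simulated data had rank 9. An 11- or 12-degree-of-freedom Wald test needs an inverse that does not exist.

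**5. With a correction.** For two visits and complete pairs, the Mancl-DeRouen standard error is the robust one × n/(n − 1) = 10/9. Referred to t(9), the test rejects when |estimate|/uncorrected SE exceeds 2.262 × 10/9 = 2.51. Simulated error is 4.3-5.0% at CV 0.53 and up to about 7.5% at CV 1.0. Interval width rises by 2.51/1.96 = 1.28. An uncorrected p of 0.05 becomes P(|t(9)| > 1.96 × 0.9 = 1.764), about 0.11.

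**The case against.** The strongest reply is that the plan names no estimator, so 10% belongs to one option among several. That is right, and the figure is conditional. In a two-visit simulation with a model-based covariance instead (CV 0.53, dispersion parameter 1), the error was 4-5% with the scale fixed at 1 and 15-17% with a Pearson scale. This limits the claim but does not remove it: from what is written, the 5% cannot be verified. Screening data for assumptions will not reveal that a sandwich variance is too small with 10 subjects. The promise to report deviations does not help where the plan leaves the choice open.

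A second reply is that the stakes are small: an uncontrolled pilot, secondary outcomes, no decision rule, and all subjects also receiving counselling and contingency management. That stands, and it sets the weight of the point.

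Four stronger readings are tempting, and the documents do not support them:

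- **A week-factor error rate of 15% to 40%.** Such figures arise for two to four contrasts. The weekly schedule gives at least 11, where the problem is that the joint test cannot be formed.
- **An unsound sample size.** The power claim rests on a mixed model for grams, and its 80% is met.
- **Other gaps making the error worse.** Amount of use appears in grams in one place and joints in another, and the follow-up timing conflicts between the Overview, the outcome list and Data analysis. These need reconciling, but they are separate consistency points and do not change the GEE error rate.
- **Replacing the GEE with a paired baseline-to-last-visit test.** The secondary outcome covers use over the study duration, so this would discard most weekly data. It would often lose power too: at CV 0.75-1.0 the paired t-test has 50-79% against 64-85% for the corrected GEE.

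**Conclusion.** The concern holds in conditional form. If the usual uncorrected robust Wald test is used with 10 subjects, a single-degree-of-freedom time effect has about 10% type I error at a nominal 5%: 9.6% in closed form and roughly 10-15% in simulation, higher with strong autocorrelation or fewer completers. A joint test of week as a factor over the weekly schedule cannot be formed properly.

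The closed form needs only n and approximate normality of the subject-level contributions. The simulated range rests on count means and dispersions that the documents do not give. The point covers only secondary outcomes sent to the GEE. In a single arm even a correct p-value speaks to change over time, not to the effect of the drug. This is a cheap and worthwhile improvement, not a threat to the primary outcomes or the sample size.

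**What to change.** Keep the negative-binomial GEE and add the following to the Data analysis section before the data are analysed:

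- For each count outcome, name one single-degree-of-freedom within-subject contrast and the visits it uses.
- Test it with a bias-corrected robust standard error (Mancl-DeRouen, for example) and a t distribution with 9 degrees of freedom.
- State that week will not be tested jointly as a many-level factor. Weekly values can still be described.
- Optionally, add a paired t or Wilcoxon signed-rank analysis as a sensitivity check.

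**Cost.** A few sentences of plan text and little analysis work, with no change to sample size or visits. GEE intervals become about 28% wider. For a 50% fall with SD unchanged (CV 0.53 at baseline), power drops from 86% uncorrected to 74-76%; if the CV stays constant instead, the corrected GEE has about 98%. Some liberality can remain under heavy dispersion (up to about 7.5%). For two visits with complete pairs the correction is hand arithmetic on standard output (multiply the SE by 10/9 and use 2.262). With more visits or incomplete pairs it may need software other than SPSS v24.0, and the plan should then name it.

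### Subjects may be withdrawn from the study for side effects or deviation with no provision for outcome collection afterwards, so primary abstinence data can be lost despite the intention-to-treat commitment

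*Combined protocol and SAP*

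**What the plan says.** The protocol and SAP are one document. Its section Termination of the Study introduces a list with "Reasons for withdrawing individual subjects from the study may include one or more of the following". Among the entries are "Severe side effects", "Major protocol deviation" and pregnancy, beside loss to follow-up and withdrawal of consent. The section adds: "Any subject may be discontinued from the study at the discretion of the investigators", where this is judged to be in the subject's best interest. In both places the subject leaves the study; stopping injections while visits continue is not mentioned.

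The Hepatotoxicity paragraph, under the risks of the medication, does speak of stopping the drug and of whether dosing should continue. It does not say what happens to the subject's visits.

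On analysis, the Data analysis section states: "All efficacy analyses will be by intention-to-treat". On missing values it says only: "In the final report the procedures used to deal with missing, unused or spurious data in statistical analyses will be described". The primary efficacy outcome there is seven-day point prevalence abstinence one week after medication ends and at the 3-month follow-up. The primary tolerability outcome, there and under Primary and Secondary Outcome Measures, counts subjects who leave because of SAEs.

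The Power calculation says that "a sample of 10 subjects will give us 80% power to detect a decrease in cannabis use of 50% from baseline to the last time" assessed, and ends with "No dropout was assumed".

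**The concern.** Intention-to-treat needs an outcome, or a stated rule in place of one, for every enrolled subject whether or not treatment continued. Here the only action described for a subject with severe side effects or a major deviation is exit from the study. A subject who exits during the medication phase has neither abstinence assessment. Removal for severe side effects is plausibly tied to treatment, and removal for deviation plausibly tied to adherence, so the missing values may be informative. There is no control arm against which a distortion could be seen, and no rule fixed in advance says how a missing abstinence status will be counted.

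The plan also expects some exits, because exit for SAEs is a primary outcome, while its power figure assumes none.

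**Working it through.** **1. Is there any route to outcomes after drug stops?** Three places were compared.

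- Termination of the Study: exit is from the study, and no later assessment is described.
- Hepatotoxicity paragraph: the drug may be stopped; visits are not mentioned.
- Summary of Study Assessments: timeline follow-back (TLFB) and urine for THC metabolites are scheduled weekly in weeks 1-16 and monthly in months 5-6. Nothing says whether these continue for a subject off drug.

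No sentence keeps such a subject in follow-up, and none says that data collection ends.

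**2. Primary outcome.** With 10 enrolled, a observed abstinent and m missing, the abstinence proportion is known only to lie between a/10 and (a + m)/10. The width is m/10: 10 percentage points for one missing subject, 20 for two, 30 for three.

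**3. The plan's power figure (secondary outcome: amount used).** Inputs from the Power calculation:

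- baseline mean 9.5 g, SD 5
- 50% decrease, so the difference is 0.5 × 9.5 = 4.75 g
- correlation 0.6
- two-sided 0.05
- mixed model with time fixed and subject random, which with two time points is equivalent to a paired t-test.

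The SD at the last time point is not given. It is assumed to be 5, with 2.5 as the alternative.

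SD of change = √(SD₁² + SD₂² − 2 × 0.6 × SD₁ × SD₂)

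- SD₂ = 5: √(25 + 25 − 30) = √20 = 4.472
- SD₂ = 2.5: √(25 + 6.25 − 15) = √16.25 = 4.031

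Power is taken from the noncentral t distribution with n − 1 degrees of freedom and noncentrality (4.75 / SD of change) × √n. At n = 10 the noncentrality is 3.359 for SD₂ = 5 and 3.726 for SD₂ = 2.5.

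| Subjects with both values | Power, SD₂ = 5 | Power, SD₂ = 2.5 |
|---|---|---|
| 10 | 84.74% | 91.11% |
| 9 | 79.65% | 87.06% |
| 8 | 73.18% | 81.45% |
| 7 | 65.14% | 73.87% |

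With SD₂ = 5, ten is the smallest sample that reaches 80%, so the sample size reproduces. The power at 10 is 84.7%, somewhat above the stated 80%. A simulation of 200,000 replications gave 84.65%.

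**4. What the table shows.** With SD₂ = 5, one lost endpoint leaves about the stated 80% and two bring power to 73.2%. With SD₂ = 2.5, two lost endpoints still leave power above 80%. The table treats a subject without a last value as contributing nothing.

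**The case against.** The list gives reasons that may apply, qualified as severe or major, so exit is permitted and not required. A reader might infer that the plan orders follow-up to end. The documents do not say so: the end of data collection is inferred from exit from the study together with silence about later visits. The Hepatotoxicity paragraph treats dosing as something that can be stopped separately, which weakens the inference but does not remove it, since it says nothing about visits.

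A reader might also infer that abstinence will be inflated, for example that 4 of 10 (40%) would be reported as 4 of 8 (50%) after two users are removed. That example is hypothetical and assumes a completer analysis. The plan commits to intention-to-treat, under which the denominator would be 10. What stands is that no rule says how the two missing subjects would be counted.

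Nor do the power figures show that the trial is underpowered. They concern a secondary outcome, rest on an unstated SD, and ignore weekly data collected before exit, which the planned GEE and mixed models can use under missingness assumptions the plan does not state. The documents support no withdrawal rate. Withdrawal of consent and loss to follow-up would cause the same loss, and no wording can prevent them.

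The strongest objection concerns the remedy. Tolerability is counted as leaving the study because of SAEs. If subjects who stop injections for an SAE stay in follow-up, they drop out of that count and tolerability looks better than it was. This is correct, and the two changes must be made together.

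Finally, this is a pilot of 10 subjects meant to show tolerability and a trend. That limits the weight of the point, but endpoints that were never collected cannot be recovered later.

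**Conclusion.** The point holds as a gap in the plan. Subjects can be removed from the study for severe side effects, major deviation or pregnancy, nothing provides for outcomes after drug stops, and the primary abstinence outcome can then be missing for treatment-related reasons under an intention-to-treat commitment that has no missing-data rule.

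The firm measure of size is that each lost subject is one tenth of the sample and adds 10 percentage points of uncertainty to the abstinence proportion. The power losses are illustrative and depend on the assumed last-visit SD. The conclusion rests on reading exit from the study, with no follow-up described, as allowing assessments to stop. It does not show that any subject will be lost, or in which direction the result would move.

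**What to change.** In Termination of the Study, separate discontinuation of study drug from withdrawal from the study. State that subjects who stop injections keep the TLFB and urine visits already scheduled, unless they withdraw consent, are lost to follow-up, or the investigator judges continued visits not to be in their best interest. In Data analysis, state that all enrolled subjects stay in the intention-to-treat denominator, and fix in advance how a missing abstinence status is counted.

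In the same change, reword the primary tolerability outcome, both under Primary and Secondary Outcome Measures and in Data analysis, to count subjects who discontinue study drug or leave the study because of SAEs. Subjects kept in follow-up are then still counted.

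None of this alters when or whether treatment is stopped. The cost is an amendment to wording, including a primary outcome definition, and some retention effort for subjects off drug. The visits are already in the schedule; the documents contain no study budget from which to cost them.
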